I agree to obtain approval of the protocol and informed consent prior to the start of the study by an Institutional Review Board (IRB)/Independent Ethics Committee (IEC) that is registered with the US Department of Health and Human Services (HHS).

I agree to obtain formal written informed consent in accordance with applicable federal and local regulations and international guidelines from all subjects prior to their entry into the study.

I have received and reviewed the Microcyn® Skin and Wound Care with Preservatives package insert, including the potential risks and side effects of the product, and instructions for use.

I agree to report to Oculus Innovative Sciences, Inc. adverse events that occur during the course of the study in accordance with the ICH GCP guideline and the protocol.

I agree to ensure that all associates, colleagues, and employees assisting me with the conduct of the study are informed of their responsibilities in meeting the above commitments and the commitments set forth in the Investigator’s Agreement.

I agree to maintain adequate and accurate records and to make those records available for inspection in accordance with the ICH GCP guideline, and federal and local requirements.

The Investigator, agreeing to the foregoing, hereby executes this agreement on the date as set forth below.

Investigator Signature

Printed Name

Date

Address

Phone Number

PROTOCOL SYNOPSIS

Name of Sponsor/Company:	Oculus Innovative Sciences, Inc.
Name of Finished Product:	Microcyn [®] Skin and Wound Care with preservatives (“Microcyn”)
Name of Active Ingredient:	N/A
Title of Study:	A Six Month Randomized Open-Label Trial of Pressure Ulcer Healing with Microcyn [®] Skin and Wound Care with Preservatives Versus Sterile Saline in Adult Spinal Cord Injury Subjects
Investigators:	[name]., PhD, [name].
Study Center:	University of Alabama at Birmingham, Spain Rehabilitation Center [name]
Number of Subjects Planned:	80 subjects
Publication (Reference):	N/A
Study Period:	Enrollment Period: Rolling enrollment to the earliest of 2 years or enrollment of 80 subjects Treatment Period: Baseline (Week 0) to Final Evaluation (earlier of 6 months = Week 24 or complete wound closure) Analysis Period: An interim analysis will be conducted when the greater of 20 patients or those enrolled in the two (2) weeks following enrollment of the first participant have completed the Week 12 visit. The full analysis is when all subjects have completed the Final Evaluation.
Phase of Development:	Post-marketing
Objective:	A pressure ulcer (wound/sore) is localized injury to the skin and/or underlying tissue usually over a bony prominence, as a result of pressure, or pressure in combination with shear and/or friction. Primary objective: To compare percentage change in ulcer size in patients with at least one Stage III or Stage IV pressure ulcer in subjects treated with Microcyn versus sterile saline. Secondary objectives: To compare healing progress using the National Pressure Ulcer Advisory Panel’s Pressure Ulcer Scale for Healing (PUSH) score, Version 3.0, and other indicators of wound healing such as time to complete wound closure, elimination of signs of wound infection and to investigate the impact of treatment with Microcyn on subject health care resource utilization (wound-related).
Clinical Hypothesis:	

Name of Sponsor/Company:	Oculus Innovative Sciences, Inc.
Name of Finished Product:	Microcyn [®] Skin and Wound Care with preservatives (“Microcyn”)
Name of Active Ingredient:	N/A
Treatment of pressure ulcers with Microcyn results in faster healing and better overall outcomes than treatment with sterile saline in spinal cord injured adults.	
Design and Methodology:	
Design: Six month (24 week), randomized, open-label, comparative study of treatment of pressure ulcers using Microcyn versus sterile saline.	
Subjects: Adults with spinal cord injuries with at least one Stage III or Stage IV pressure ulcer who meet all eligibility criteria and who have given informed consent.	
Treatment: Microcyn or sterile saline liberally sprayed on wound and permitted to remain on wound which will then be dressed with gauze that is moistened with Microcyn or sterile saline and covered with dry gauze twice daily for the earlier of total wound closure or Week 24.	

Study Visits:

Overall: Assessments will be made at Week 0 (Baseline) with follow-up visits every 4 weeks thereafter, for a total of up to 7 study related assessments (Week 0 (Baseline), Weeks 4, 8, 12, 16, 20 and Week 24 (Final Evaluation)). Subjects will return to the clinic for all follow-up assessments.

Baseline: Initial demographics and a brief medical history will be collected at Baseline from subjects or via chart abstraction after informed consent and after meeting all inclusion/exclusion criteria. Data on the primary endpoint will be collected: pressure ulcer size (stage, length, width, and depth) via clinician measurement with photographic documentation. Secondary endpoints of infection status of the ulcer including signs/symptoms of infection, amount and type of exudates, color and type of tissue/character of the wound bed and health care resource utilization (wound-related) and adverse events will also be collected at Baseline. The wound surface area (length x width), amount of exudate and tissue type will be recorded using the PUSH Tool 3.0, and a PUSH baseline score will be calculated (PUSH score).

Follow-up visits: Information collected at each follow up visit will include information on the pressure ulcer size (length, width, depth via clinician measurement with photographic documentation), PUSH sub-scores and total score, time to complete closure of wound, infection status of the ulcer including signs/symptoms of infection, health care resource utilization (wound-related) and adverse events. If applicable, reason for early discontinuation will be recorded. Treatment-related adverse events will be collected at all follow-up visits.

Procedures	Baseline	Follow-Ups	Final Evaluation
Study procedures			
Informed Consent and Privacy Authorization	X		
Inclusion/Exclusion Criteria	X		
Demographics			
Age, Race, Gender, Education, Insurance Status (from chart)	X		
Marital, Employment, Insurance Status			
Medical History			
Height, Weight, Smoking/Tobacco Status	X		
Spinal Cord Injury Information (from chart)	X		
Type of Bladder Management	X		
Number of Concomitant Ulcers	X	X	X
Use of Antibiotics	X	X	X
Primary efficacy endpoint			
Ulcer Depth, Length, Width, Stage	X	X	X
Secondary endpoints			
Wound Infection Status	X	X	X
Amount and Type of Exudate	X	X	X
Color/Type of Tissue/Character of Wound Bed	X	X	X
PUSH Scores	X	X	X
Health Care Resource Utilization (Wound-Related)		X	X
Safety			
Reason for Early Discontinuation (if applicable)		X	
Adverse Events	X	X	X

Name of Sponsor/Company:	Oculus Innovative Sciences, Inc.
Name of Finished Product:	Microcyn [®] Skin and Wound Care with preservatives (“Microcyn”)
Name of Active Ingredient:	N/A
Safety Evaluations:	
Adverse Events (AEs) will be recorded at Baseline (pre- and post-application) and at each study visit.	
Efficacy Evaluations:	
Primary Endpoint: The primary endpoint is pressure ulcer size (length, width, depth via clinician measurement with photographic documentation). Secondary Endpoints: Secondary endpoints include healing progress, as measured through the NPUAP PUSH Tool, Version 3.0, time to complete wound closure, infection status of the ulcer including signs/symptoms of infection, amount and type of exudates, color and type of tissue/character of the wound bed, health care resource utilization (wound-related), and adverse events.	
Diagnosis and Main Eligibility Criteria:	
Inclusion Criteria:	

 – Written informed consent including authorization to release health information – Male or female (non-pregnant/nursing) outpatients over the age of 18 – Spinal cord injured – One or more Stage III or Stage IV pressure wound located anywhere on the body – Willing and able to fulfill all obligations of the study, including attending all study visits and has the ability him/herself or via a caregiver to apply study product twice daily 	
Exclusion Criteria:	

 – Patient has any wound that at enrollment is scheduled for surgical closure within 14 days – Use of any immunosuppressant medications (for example, cyclosporine, methylprednisolone, prednisone, methotrexate, alefacept, or infliximab) within 30 days of screening – Is unable to fully comply with the study requirements; for example, if the wound is in a place that the patient cannot reach him/herself and as such requires a caregiver to apply the study product, if the patient does not have consistent twice daily access to a caregiver, this patient would be ineligible for the study – Any condition or situation which, in the Investigator’s opinion, puts the subject at significant risk, could confound the study results, or may interfere significantly with the subject’s participation in the study – Patient is medically unstable or has a life expectancy of less than 12 months – Patient is pregnant – Patient is a woman of child-bearing potential and does not consent to or receive a screening urine pregnancy test prior to study enrollment – Current enrollment in an investigational drug or device study or participation in such a study within the last 30 days prior to Baseline (Week 0) 	

Name of Sponsor/Company:	Oculus Innovative Sciences, Inc.
Name of Finished Product:	Microcyn [®] Skin and Wound Care with preservatives (“Microcyn”)
Name of Active Ingredient:	N/A
Test Article, Dose, and Mode of Administration:	
Microcyn [®] Skin and Wound Care with preservatives, applied twice daily, topical administration	
Statistical Analyses:	
Efficacy Analyses:	
Efficacy will be tested via T-tests of percent change in wound size using an intention to treat (ITT) approach as well as a per protocol analysis. Secondary analyses will include Kaplan-Meier analysis to estimate time to complete wound closure, and may include linear and logistical regression to estimate the impact of patient characteristics on study endpoints, with special emphasis on variables that affect healing times, such as diabetes and smoking status. The efficacy population will include all patients entered into the study.	
Safety Analyses:	
Safety analyses will be conducted via Fischer’s exact tests, chi-square, and t-tests, as applicable. The safety population will include all subjects exposed to the any study product (Microcyn or saline) who have provided any post-treatment safety information.	
Sample Size Justification:	
The sample is a convenience sample of 80 patients.	

LIST OF ABBREVIATIONS AND DEFINITIONS OF TERMS

Abbreviation	Definition
AE	Adverse Event
ASIA	American Spinal Cord Injury Association
CFR	Code of Federal Regulations
CTEP-	Cancer Therapy Evaluation Program – Common Terminology Criteria for
FDA	Food and Drug Administration
GCP	Good Clinical Practices
HHS	Health and Human Services
ICH	International Conference on Harmonisation
IEC	Independent Ethics Committee
IRB	Institutional Review Board
ITT	Intention To Treat
MedDRA	Medical Dictionary for Regulatory Activities
NPUAP	National Pressure Ulcer Advisory Panel
PUSH	Pressure Ulcer Scale for Healing
SAE	Serious Adverse Event
SAS	Statistical Analysis Software
SOP	Standard Operating Procedure
UPT	Urine Pregnancy Test
US	United States
WOCBP	Woman of Childbearing Potential

COVER PAGE ERROR! BOOKMARK NOT DEFINED.

SIGNATURE PAGE 2

INVESTIGATOR'S AGREEMENT 3

PROTOCOL SYNOPSIS..... 4

LIST OF ABBREVIATIONS AND DEFINITIONS OF TERMS..... 9

1. INTRODUCTION AND BACKGROUND..... 12

 1.1. STUDY RATIONALE 15

 1.2. DOSE RATIONALE 16

 1.3. STUDY OBJECTIVE..... 16

 1.4. CLINICAL HYPOTHESES..... 16

2. STUDY DESIGN..... 17

 2.1. OVERALL DESIGN..... 17

 2.1.1. *Structure*..... 17

 2.1.2. *Duration* 17

 2.1.3. *Controls*..... 17

 2.1.4. *Dosage/Dose Regimen*..... 17

 2.2. TEST ARTICLE 17

 2.3. STUDY POPULATION 17

 2.4. ELIGIBILITY CRITERIA..... 17

 2.4.1. *Informed Consent and Authorization to Release Health Information*..... 17

 2.4.2. *Inclusion Criteria*..... 19

 2.4.3. *Exclusion Criteria*..... 19

3. STUDY PROCEDURES AND METHODS..... 21

 3.1. SUBJECT ENTRY PROCEDURES..... 21

 3.2. SCHEDULE OF VISITS AND PROCEDURES 21

 Table 1: Schedule of Visits and Procedures 21

 3.2.1. *Baseline Visit* 21

 3.2.2. *follow-up visits (Weeks 4, 8, 12, 16, 20)*..... 24

 3.2.3. *subject application instructions*..... 26

 3.2.4. *subject restrictions* 26

 3.2.5. *Discontinuation/Withdrawal Procedures*..... 26

 3.3. VARIATION FROM SCHEDULED VISIT DAYS..... 27

 3.4. SAFETY ASSESSMENTS 27

 3.4.1. *adverse events*..... 27

 3.5. EFFICACY ASSESSMENTS..... 27

 3.5.1. *Time to wound closure*..... 27

 3.6. SCREEN FAILURES..... 27

 3.7. PROTOCOL DEVIATIONS..... 28

4. PROHIBITED MEDICATIONS AND TREATMENTS..... 29

Table 2: Prohibited Medications and Treatments	29
5. EVALUATION OF ADVERSE EVENTS.....	30
5.1. DEFINITIONS.....	30
5.1.1. Adverse Event Severity Grades	32
5.1.2. Study product Causality	33

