2.1.2. DURATION

The study duration is up to 6 months (24 weeks) per subject with an enrollment period of up to two years to enroll a total of 80 subjects.

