2.1.4. DOSAGE/DOSE REGIMEN

Treatment with Microcyn or saline will consist as follows, twice daily: Microcyn or sterile saline to be liberally sprayed on wound and permitted to remain on wound, which will then be dressed with gauze moistened with Microcyn or sterile saline and covered with dry gauze twice daily for the earlier of complete wound closure or Week 24.

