3.2.5. DISCONTINUATION/WITHDRAWAL PROCEDURES

A subject may voluntarily withdraw from study participation at any time for any reason. If the subject withdraws consent and discontinues from the study, the Investigator will attempt to determine the reason for discontinuation and record the reason in the subject’s records. If a subject withdraws consent because of an AE, that AE should be indicated as the reason for withdrawal. In the event of early discontinuation, (i.e., prior to the earlier of complete wound closure or Week 24) and whenever possible, the subject should be asked to return to the study center to complete the final evaluations. Subjects who withdraw from the study will not be replaced.

If at any time during the study, the Investigator determines that it is not in the best interest of the subject to continue, the subject will be discontinued from participation. The Investigator can discontinue a subject at any time if medically necessary. The Investigator may discontinue a subject’s participation if the subject has failed to follow study procedures or to keep follow-up appointments. Appropriate documentation in the subject’s study record regarding the reason for discontinuation must be completed.

All subjects who fail to return to the study center for follow-up for any visit will be contacted by phone and/or email to determine the reason(s) why the subject failed to return for the necessary visit or elected to discontinue from the study. If a subject is unreachable

by telephone after a minimum of two documented attempts (one attempt on two different days), a registered letter (with duplicate sent by first class mail, postage prepaid) will be sent requesting that contact be made with the Investigator. Only after these attempts have failed will a subject be deemed lost to follow-up.

This study may be terminated in accordance with the Clinical Trial Agreement. Should this be necessary, both Oculus and the Investigator will ensure that proper study discontinuation procedures are completed.

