3.5.1. TIME TO WOUND CLOSURE

Time to wound closure will be defined as date from Baseline assessment to the date the patient reports the wound closed or the first time the wound is visually documented to be closed by the investigator at a study visit, whichever comes first. If the patient reports the wound to be closed between study visits, the investigator must confirm closure of the wound at the next study visit and note the exact date of wound closure, as reported by the patient, on the subject's clinic record.

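### A wound first seen closed at a visit before Week 24 need not be measured again, so a later re-opening would go unseen in the primary endpoint and in time to closure.

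*Combined protocol and SAP*

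**What the plan says.** **Text that lets a patient finish at closure**

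- Synopsis, Study Period: the treatment period runs to "Final Evaluation (earlier of 6 months = Week 24 or complete wound closure".
- Synopsis, Study Visits, and Section 2.1.2 give maxima, not fixed numbers: "for a total of up to 7 study related assessments" and "The study duration is up to 6 months (24 weeks) per subject".
- Section 2.1.4: treatment is given "for the earlier of complete wound closure or Week 24".
- Section 3.2.5 defines who has left early: "In the event of early discontinuation, (i.e., prior to the earlier of complete wound closure or Week 24) and whenever possible". A patient who leaves at closure has therefore completed the study.

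**How closure is defined and checked.** Section 3.5.1 dates closure from the patient's report "or the first time the wound is visually documented to be closed by the investigator at a study visit, whichever comes first". For closures reported between visits, "the investigator must confirm closure of the wound at the next study visit". No check is required after a closure that the investigator first sees at a visit. No section defines sustained closure, schedules a measurement after closure, or mentions re-opening.

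**How the data are used.** Section 6.3.1 compares percent change in wound size by t-test. It names no time point and gives no rule for patients who finish early. Time to closure is analysed by Kaplan-Meier and also drives the interim rule for halting for success.

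**Text that points the other way.** Section 6.1 has all 80 patients completing Week 24 assessments, which it equates with the Final Evaluation. Section 5.1 sets an adverse event window of Weeks 0 to 24 for each patient. Section 3.2.2 lists Week 24 procedures, and Section 3.3 asks that patients be kept to a 24-week schedule.

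**The concern.** Pressure ulcers in this population arise from immobility and impaired sensation (Section 1). Both persist after a wound closes, so re-opening within the 24 weeks is plausible. The plan does not clearly provide for seeing it.

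The closure call is made by someone who knows the treatment, and that call can itself end observation. A lenient call would then never be exposed by a later measurement. The last size on record would be zero, taken at closure, and would enter the primary comparison beside sizes taken at Week 24. Time to closure would count the same wound as healed. The interim halting rule uses that endpoint when few closures are likely, so one or two short-lived closures could matter. Measurements not taken cannot be recovered at analysis.

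**Working it through.** There is no plan figure to reproduce. The 80 patients are a convenience sample, and the documents give no power, standard deviation, closure rate or re-opening rate for this trial.

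**1. Unobserved time.** For a wound first seen closed at week w, the unobserved time is 24 - w weeks, or (24 - w)/4 scheduled visits.

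| First seen closed | Weeks unobserved | Visits not made |
|---|---|---|
| Week 4 | 20 | 5 |
| Week 8 | 16 | 4 |
| Week 12 | 12 | 3 |
| Week 16 | 8 | 2 |
| Week 20 | 4 | 1 |

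**2. Closures to expect.** The only background figure is in Section 1: in a retrospective review of veterans with spinal cord injury, over 50% of ulcers had not fully healed in three years (156 weeks). Taking 50% and assuming a constant rate:

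- by Week 24: 80 × (1 - exp(-24 × ln2/156)) = 80 × 0.101 = 8.1 closures
- by Week 12, among 20 interim patients: 20 × (1 - exp(-12 × ln2/156)) = 1.04 closures

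Because the source says over 50%, 8.1 is the upper end under that assumption. The Stage IV figure in the same section (over 70% unhealed) gives at most 80 × (1 - exp(24 × ln(0.7)/156)) = 4.3.

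**3. Size in one arm, with cost on the same closure rates.** Let p be the share closed, r the share of those re-opened by Week 24, and L the re-opened size as a share of baseline volume. The closed proportion is overstated by p × r. If closed wounds enter at -100%, mean percent reduction is overstated by 100 × p × r × L points. I assume r = 10% to 30%, L = 30%, and closure around Week 12, so 3 visits remain for each closed wound.

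| | p about 10% (8.1 of 80) | p = 40% (32 of 80) |
|---|---|---|
| Patients re-opened, whole trial | 0.8 to 2.4 | 3.2 to 9.6 |
| Closed proportion overstated (points) | 1 to 3 | 4 to 12 |
| Mean reduction overstated (points) | 0.3 to 0.9 | 1.2 to 3.6 |
| Added visits | 8.1 × 3 = about 24 | 32 × 3 = 96 |

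**4. Direction between arms.** Suppose first closure is 50% against 30%, a difference of 20 points (illustrative).

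| Re-opening | Closed at Week 24 | Difference |
|---|---|---|
| 20% and 20% | 40% and 24% | 16 points |
| 30% and 10% | 35% and 27% | 8 points |
| 10% and 30% | 45% and 21% | 24 points |

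First closure can overstate or understate the difference at Week 24.

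**The case against.** The strongest reply is that the plan can be read as following everyone to Week 24. The synopsis calls Week 24 the Final Evaluation, and Sections 3.2.2, 3.3, 5.1 and 6.1 all fit that reading. It is a fair reading of those sections, and it means that one cannot say flatly that follow-up ends at closure. But none of them says that a closed wound is measured again, and the synopsis and Section 3.2.5 let the patient finish. What stands is an unreconciled conflict, and a site that follows the synopsis complies with the plan.

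Second, part of the gap is already covered. A closure reported between visits must be confirmed at the next visit, so a re-opening before that visit should be caught. That stands, and it limits the point to closures first seen at a visit and to re-opening after a confirmed closure.

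Third, first closure is a coherent endpoint for a hypothesis about faster healing, and no objective claims durable closure at six months. That also stands, and it is a reason to keep first closure as the event. It does not settle how a re-opened wound should count in the primary percent change.

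Fourth, treatment ends at closure, so a Week 24 size in a re-opened wound partly reflects later care. This is true, and the estimate should say so.

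Last, requiring every closure to be confirmed at the next visit would lose closures first seen at Week 24, and those first seen at Week 12 when the interim analysis is triggered. The objection is sound, and the fix must allow for it.

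**Conclusion.** The point holds in a limited form. The plan permits a wound first seen closed at Week 4 to 20 to go unmeasured afterwards, and its sections disagree on whether that patient is followed to Week 24. Re-opening would be missed in both the primary endpoint and time to closure.

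At the protocol's background healing rate the effect is small: about 1 to 2 patients, 1 to 3 points on the closed proportion and 0.3 to 0.9 points on mean reduction. This rests on a constant healing rate, 10% to 30% re-opening and re-opened wounds at 30% of baseline volume. The documents supply none of these three.

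A reader might infer three stronger things that the documents do not support:

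- **That the plan scores closed wounds as -100%.** Section 6.3.1 names no time point and no carry-forward rule. The value is an inference from a last size of zero. The alternative, a missing Week 24 value, has no rule either.
- **That everyone else is measured at Week 24.** Patients who discontinue early are asked to return for final evaluations when they leave.
- **That the bias favours Microcyn, or the arm with more closures.** This depends on the re-opening rate in each arm, which is unknown, and the direction can go either way.

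**What to change.** 1. Reconcile the synopsis and Section 3.2.5 with Sections 5.1 and 6.1. State that patients whose wound closes still attend the remaining scheduled 4-weekly assessments to Week 24, for measurement only and with no change to the treatment rules.
2. In Section 6.3.1, take the primary percent change for the final analysis at Week 24 for every patient, whatever care followed closure.
3. Keep first closure as the time-to-closure event, so the endpoint used by the interim rule keeps its meaning.
4. Add an analysis that counts a closure only if the wound is still closed at the next scheduled visit, dated back to first closure. In that analysis, closures first seen at Week 24, or at the last visit available at the interim, count on that visit alone and are flagged as unconfirmed.

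The cost is amendment wording and added travel for healed patients: about 24 visits at about 10% closure and up to about 96 at 40%. All fall within the seven visits already planned for each patient.
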